1 STUDY SYNOPSIS

Sponsor / Sponsor- Investigator	[name]. med. [name]
Study Title	Prognostic Impact of Physical activity patterns after percutaneous coronary intervention- PIPAP study
Short Title / Study ID	PIPAP study
Protocol Version and Date	Version 1.3 (dated 18/11/2020)
Study Registration	ClinicalTrials.gov
Study Category and Rationale	A, no intervention, only monitoring for risk prediction
Background and Rationale	Physical activity monitoring after coronary bypass grafting and other major surgeries has been found to be predictive for hospital readmission and adverse outcome. In patients after percutaneous coronary intervention (PCI) it has been found that a patient reported activity score is predictive of 3 year major adverse coronary event (MACE). It is not known whether physical activity shortly after discharge from PCI is predictive of one-year MACE. Early identification of patients at increased risk of MACE would facilitate the intensification of preventive strategies in these patients.
Risk / Benefit Assessment	Wearing an activity tracker for two weeks following hospital discharge bears no risk. Early identification of patients at increased risk of MACE would benefit these patients as they can be followed-up more closely and more emphasis can be put on adherence to medication and other preventive strategies (e.g., smoking cessation).
Objective(s)	Primary objective is the quantification of physical activity (daily steps) during the first two weeks after hospital discharge as a predictor for MACE at one year. Secondary objectives are: 1) Comparison between daily steps and objectively measured activity counts (divided in time spent in moderate-to-vigorous activity, light activity and sedentary activity), as well as patient reported activity; 2) Association of daily steps after one year with reaching targets for systolic blood pressure, low-density lipoprotein cholesterol (LDL-C), body mass index (BMI) and glycated haemoglobin (HbA1c); 3) comparison of daily steps after hospital discharge and MACE between non cardiac rehabilitation (CR), conventional hospital based CR, tele-CR and modular CR participants; 4) comparison of daily steps at one year after hospital discharge in different CR groups.
Endpoint(s)	Primary endpoint: MACE at one year after PCI. Secondary endpoints: BMI, systolic BP, LDL-C, HbA1c 12 months after PCI; daily steps and activity level two weeks and 12 months after PCI hospital discharge; proportion and patient characteristics of CR participants and non-participants
Study Design	Observational single centre study.
Statistical Considerations	Predictive value of daily steps during the first two weeks after hospital discharge is quantified by net reclassification improvement (NRI) and by increase of area under the curve (AUC) of the receiver operating characteristic curve (ROC) of a model consisting of traditional risk factors (age, sex, cardiovascular risk factors, cardiovascular history, comorbidities).
Inclusion- / Exclusion Criteria	Inclusion criteria: Patients after PCI younger than 80 years of age who are eligible for ambulatory CR. Exclusion criteria are inability to participate in ambulatory CR (nursing home residence, stationary CR, orthopedic or neurologic impairment prohibiting physical exercise, psychiatric conditions), and staged PCI.
Number of Participants with Rationale	The sample size is based on a previous study who found a significant difference between the quartile with lowest versus highest self-reported physical activity on MACE at 3 years after PCI. Based on this, we would need 33 events to reach a significance level of 0.05 and a power of 80% in these two quartiles or 66 events in the whole sample. According to data from CARDIOBASE Bern PCI registry, we can expect 100 MACE per year in approximately 1200 patients younger than 80 years of age undergoing PCI at our centre. If we assume that

	50% of these patients are willing to participate in our study, we could recruit about 800 patients in 16 months, who will have approximately 66 MACE within one year.
Study Intervention	Patients will be provided with an activity tracker in the form of a wrist band that they should wear continuously for two weeks after hospital discharge. After 12 months, they will be asked to wear the activity tracker again for two weeks in case they attend the clinical routine check-up in our institution.
Control Intervention	None
Study procedures	Patients will receive the wrist band, the patient information sheet including informed consent (IC), the international physical activity questionnaire - short form (IPAQ-SF), and an addressed and prepaid envelope before hospital discharge. They are asked to read the patient information when arrived at home, sign the IC when willing to participate and wear the wrist band for two weeks. After that, they should complete the IPAQ-SF, send the wrist band and signed IC to our institute. Patients who do not want to participate in the study are asked to send back the activity tracker to our institution without signing the IC. Health related data and information regarding CR uptake will be derived from the clinic's patient information system for all patients who have either signed the study IC or have not withdrawn the clinics' general informed consent to further use of data for research. MACE, patient characteristics, patient history, risk factors and comorbidities will be extracted from CARDIOBASE Bern PCI registry (ClinicalTrials.gov Identifier: NCT02241291). Patients attending the clinical routine check-up after 12 months in our institution will be asked to wear the activity tracker again for two weeks.
Study Duration and Schedule	Recruitment will last for 16 months. 10/2020 First-Participant-In 04/2023 Last-Participant-Out
Investigator(s)	[name]. med. [name] Leitender Arzt und Zentrumsleiter Präventive Kardiologie & Sportmedizin Universitätsklinik für Kardiologie, Inselspital, [name] [contact] [contact] PD Dr. [name] Forschungsleiterin Präventive Kardiologie & Sportmedizin Universitätsklinik für Kardiologie, Inselspital, [name] [contact] [contact]
Study Center(s)	Präventive Kardiologie & Sportmedizin Universitätsklinik für Kardiologie, Inselspital, [name]
Data privacy	Patients will be coded and code key will be stored in secure place.
Ethical consideration	Many studies have found a strong association between physical activity and survival. Some recent studies with patients after major surgery have found daily steps/physical activity level to be a strong predictor for MACE after hospital discharge. If this can be confirmed in patients after PCI, then step monitoring will be an easy, cheap and unintrusive routine clinical assessment to identify patients at high risk for MACE, who consequently can be followed up more closely.
GCP Statement	This study will be conducted in compliance with the protocol, the current version of the Declaration of Helsinki, the ICH-GCP, the HRA as well as other locally relevant legal and regulatory requirements.

2 BACKGROUND AND RATIONALE

Association of step/activity count on hospital readmission

Number of steps during the three last days of hospital stay after coronary artery bypass grafting has been found to be the strongest predictor for 30-day cardiac rehospitalisation.(1) Likewise, in patients hospitalised for decompensated heart failure, physical activity within the first week after hospital discharge was predictive of 30-day hospital readmission.(2) Slow gait speed measured in the home setting one month after acute myocardial infarction (MI) was found to be associated with a hazard ratio of 1.76 (95% confidence interval 1.08-2.87) for hospital readmission or death within one year when adjusted for age and sex.(3) In older patients (>75 years) after acute MI, functional mobility at hospital discharge was the strongest predictor for 30-day hospital readmission.(4) Interestingly, in-hospital walking activity was found to be more predictive of 30-day rehospitalisation than in-hospital activities of daily living function in older acutely ill patients.(5) Furthermore, self-reported physical activity significantly improved the prediction of 3-year MACE over traditional risk factors in patients after elective PCI.(6)

Step counting versus activity counts

Current recommendations for cardiovascular patients by the European Society for Cardiology include 150 min a week of moderate intensity or 75 min a week of vigorous intensity aerobic PA or an equivalent combination thereof.(7) In the 1960, a Japanese pedometer company launched the 10,000 steps per day promotion, which has since been found to be an appropriate recommendation.(8, 9) In older adults, a recommendation of 7,000-10,000 has been suggested to be appropriate. In order to reach an activity level that corresponds to at least moderate, a cadence of at least 100 steps/min has to be reached.(for review see Tudor-Locke et al.(10)) Therefore, half an hour of moderate activity corresponds to at least 3000 steps. However, there are no evidence based recommendation with regard to intensity level in older adults.(9) In fact, daily step count has been found to be associated with disease severity in patients with hypertrophic cardiomyopathy, while activity counts were not.(11)

Step/activity counts during CR

According to a study by Savage and Ades,(12) over 60% of patients at a mean of 36 days after PCI or CABG were sedentary (performing less than 5,000 steps/day), and less than 15% performed more than 10,000 steps/day. Activity counts per minute increased by 12% from the first to the last week of a 4-6-week cardiac rehabilitation (CR) programme.(13) In a randomised controlled trial with patients after recent MI randomised to a home-based CR programme or usual care, patients of the intervention group increased their activity counts per minute by 89% over the 3-month CR while there was no change in activity counts in the control group. (14) Both of these studies were based on small sample sizes and included a maximum of 30 patients. Sixty-four CR patients were randomised to a 3-month tele-rehabilitation programme provided by a hospital, a community health care centre or a call centre. Steps per day increased by 34% from the beginning of the tele-rehabilitation programme to one year, with no differences between the three CR providers.(15)

Tele-rehabilitation vs. centre-based CR

A recent review found tele-rehabilitation to be more successful at reducing hospital readmission and adverse events due to cardiovascular events and also for adhering to physical activity recommendations than conventional CR.(16) However, from many articles included in this review it was not clear whether tele-rehabilitation was implemented in phase II or phase III rehabilitation. A telerehabilitation programme after phase II CR in CAD patients was found to further increase exercise capacity and to reduce hospital readmission during one year follow-up by trend.(17) An older review of 2010 found no differences between home- and centre-base rehabilitation with regard to quality of life, mortality and rehospitalisation, nor cost-efficiency.(18) However, a more recent study has found tele-rehabilitation to be less cost-efficient than conventional rehabilitation.(19) More recent studies comparing tele-rehabilitation vs. centre-based conventional ambulatory rehabilitation in phase II are rare. There is one ongoing RCT in phase II

aiming at including and randomising 300 CAD patients.(20) Similar results were found for tele-rehabilitation compared to conventional CR with regard to motivation for keeping a healthy lifestyle, depression, anxiety and quality of life in 136 randomly assigned cardiac patients.(21) A non-randomised observational study has compared 24 tele-rehabilitation patients with 53 matched patients performing conventional CR during a later time period and has found similar results for physical activity assessed by questionnaire and quality of life.(22)

Risk prediction for major adverse cardiovascular event (MACE)

For patients with cardiovascular disease many instruments are available to calculate a risk score in order to estimate a patient's risk for death or reoccurring events. The RISK-PCI Score can be used for prediction of one-year adverse cardiovascular events in STEMI patients after PCI.(23) The GRACE score allows an in-hospital mortality risk assessment of patients with acute myocardial infarction as well as mortality risk assessment for up to 3 years.(24) It takes into account age, heart rate, systolic blood pressure, creatinine, abnormalities of ECG or cardiac enzymes, and signs of heart failure. The SMART risk score predicts the 10-year risk for recurrent vascular events in patients with previous cardiovascular disease.(25) Additional to age, sex, systolic blood pressure and smoking status, it takes into account history of cardiovascular disease and diabetes, as well as laboratory results of lipid status, kidney function and inflammation.

Based on the predictive value of daily steps for risk prediction found in some recent studies in various patient groups after surgery, we aim to assess the value of daily steps in patients with recent PCI in improving currently used risk assessment tools for MACE. Further, we aim to monitor whether patients enrolling in CR have higher step counts and fewer MACE than those not enrolling in CR, and whether there is a difference with regard to step counts in patients enrolling in different types of CR (conventional hospital-based CR, tele-CR, module-based CR).

3 STUDY OBJECTIVES AND DESIGN

3.1 Primary objective and hypothesis

Quantification of physical activity (daily steps) during the first two weeks after hospital discharge as a predictor for MACE at one year.

Hypothesis I: Daily steps measured during the first two weeks after hospital discharge from PCI is a significant independent predictor additional to traditional risk factors for MACE at one year after PCI.

Secondary objectives and hypothesis

1. Comparison between daily steps and objectively measured activity counts (divided in time spent in moderate-to-vigorous activity, light activity and sedentary activity), as well as patient reported activity:

Hypothesis I: Objectively monitored activity counts two weeks after hospital discharge is significantly associated with daily step counts and self-reported activity level

Hypothesis II: Predictive value of daily step count during the first two weeks after hospital discharge is significantly better than the predictive value by patient reported physical activity for MACE at 12 months.

2. Association of daily steps after one year with reaching targets for systolic blood pressure, low-density lipoprotein cholesterol (LDL-C), body mass index (BMI) and glycated haemoglobin (HbA1c):

Hypothesis I: Patients with higher daily step counts during the first two weeks after hospital discharge have higher achievement rates of target levels at 12 months for blood pressure, body weight, blood lipids, and blood sugar.

3. Comparison of daily steps after hospital discharge and MACE between non cardiac rehabilitation (CR), conventional hospital based CR, tele-CR and modular CR participants.

Hypothesis I: Tele-rehabilitation and conventional CR patients achieve higher daily step counts (corrected for age, risk factors and comorbidities) at two weeks after PCI than patients who decline any form of CR.

Hypothesis II: Tele-rehabilitation and conventional CR patients a lower risk of MACE within one year than patients who decline any form of CR

4. Comparison of daily steps at one year after hospital discharge in different CR groups.

Hypothesis I: Tele-rehabilitation is not inferior to conventional ambulatory cardiac rehabilitation (CR) in increasing daily steps from two weeks after PCI to 12 months after PCI

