3.2 Primary and secondary endpoints

Primary endpoint: Occurrence of MACE within 12 months after PCI

Secondary endpoints: BMI, systolic BP, LDL-C, HbA1c and daily steps two weeks and 12 months after PCI; proportion and patient characteristics of CR participants and non-participants

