5 STATISTICS AND METHODOLOGY

5.1. Statistical analysis plan and sample size calculation

Predictive value of daily steps during the first two weeks after hospital discharge is quantified by net reclassification improvement (NRI) and by increase of area under the curve (AUC) of the receiver operating characteristic curve (ROC) of a model consisting of traditional risk factors (age, sex, cardiovascular risk factors, cardiovascular history, comorbidities).

Descriptive statistics are used to quantify and characterise the populations who choose conventional hospital based CR, tele-rehabilitation, and modular CR in terms of number, age, sex, medical history, cardiovascular risk factors and comorbidities. MACE at one year follow-up and daily steps during the first two weeks after hospital discharge will be compared between the CR and non CR participants using multivariate modelling adjusted for potential confounding factors. Further, for patients who perform their yearly routine follow-up visit at our centre, data on body mass index (BMI), systolic blood pressure (BP), low-density lipoprotein cholesterol (LDL-C) and smoking cessation will be derived from the clinic's patient information system and compared between different forms of CR. Also, daily steps after 12 months from patients who volunteer to monitor steps again will be quantified for the different CR groups and tested between the groups if sufficient data can be gathered. The same will be done for changes in daily steps between the first two weeks after hospital discharge and at 12 months.

Sample Size:

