8.2 Data recording and source data

Data from the activity trackers will be downloaded and stored in Redcap. Questionnaires on physical activity will be manually entered into Redcap.

At the end of the study, data from this study will be merged with data from Cardiobase PCI registry, namely data on patient anthropometrics, cardiovascular history, indication for and interventions of the index PCI, comorbidities and cardiovascular risk factors, and MACE at one year follow-up. Data on choice of CR and compliance with CR and health related data will be available from the clinical data base of the unit for Preventive Cardiology and Sports Medicine of the Inselspital.

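### Secondary objective 2 judges target achievement at 12 months without using the value at the index PCI, so patients already at target count as achievers

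*SAP*

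**What the plan says.** - **Hypothesis.** Section 3.1, in the hypothesis under secondary objective 2, states: "Patients with higher daily step counts during the first two weeks after hospital discharge have higher achievement rates of target levels at 12 months". The measures are blood pressure, body weight, blood lipids and blood sugar. No index value, threshold or adjustment is mentioned.
- **Objective.** The synopsis, and the heading of objective 2 in section 3.1, use a different exposure: "Association of daily steps after one year with reaching targets for systolic blood pressure".
- **Endpoints.** The synopsis gives the risk factors at one time point: "Secondary endpoints: BMI, systolic BP, LDL-C, HbA1c 12 months after PCI". Section 3.2 has "BMI, systolic BP, LDL-C, HbA1c and daily steps two weeks and 12 months after PCI". This can be read as two time points for every measure or for steps only.
- **Analysis.** Section 5.1 takes 12-month BMI, systolic BP, LDL-C and smoking cessation, in patients who return for the yearly visit, from the "patient information system and compared between different forms of CR". It describes no analysis of steps against targets.
- **Adjustment elsewhere.** The primary hypothesis tests steps over and above traditional risk factors. Objective 3 Hypothesis I is "corrected for age, risk factors and comorbidities". In section 5.1, MACE and early steps "will be compared between the CR and non CR participants using multivariate modelling adjusted for potential confounding factors".
- **Index data.** Section 8.2 merges registry data, "namely data on patient anthropometrics, cardiovascular history" and cardiovascular risk factors among them, but does not link them to this endpoint.

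**The concern.** *Reaching* and *achieving* a target describe a change from not being there. Status at 12 months alone does not show this. Someone of normal weight at the index PCI, or without diabetes and with an HbA1c that was never raised, is scored as a success with no change at all.

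This matters because weight at the time of PCI and walking in the following two weeks may be related before follow-up begins. If they are, the more active group starts with more patients at target, and the 12-month comparison carries that difference forward. The study could then report that active patients attain their risk-factor targets more often, when the data show only that they started closer to them.

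**Working it through.** **The plan's own figure.** Objective 2 has no sizing and no assumed target rates, so there is nothing to reproduce for it. The only sizing is for MACE, and it reproduces: 4 × (1.960 + 0.842)² / (ln 2.66)² = 31.4 / 0.957 = 32.8, so 33 events in two quartiles, 66 overall, and 66 / 0.08 = 825 patients. The present point does not depend on it.

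Both illustrations below use **assumed inputs**, because the document gives none. In both, steps have no effect on change.

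**Illustration 1: BMI.** Assumptions:

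- index BMI has mean 27.5 and SD 4.5;
- the correlation r with steps is -0.05 to -0.35;
- 12-month BMI = index BMI + random change with SD 1.5;
- the cut-off is 25, as an example only and not a proposed target.

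Results from 2 million simulated patients:

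| r | below 25 at 12 months, lowest step quartile | highest step quartile | odds ratio |
|---|---|---|---|
| -0.05 | 27.8% | 31.9% | 1.2 |
| -0.15 | 23.7% | 36.4% | 1.8 |
| -0.25 | 19.8% | 40.9% | 2.8 |
| -0.35 | 16.0% | 45.6% | 4.4 |

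Example for r = -0.35: (0.456/0.544) / (0.160/0.840) = 0.838 / 0.190 = 4.4.

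- About 84% of those below the cut-off at 12 months were already below it at index. With a change SD of 3 this falls to 69%.
- With index BMI as a covariate, the step coefficient is essentially zero (probit, -0.02 to +0.003).
- Restricting to patients not at target at index, *without* the covariate, still leaves odds ratios of 1.4 (r = -0.15) to 2.3 (r = -0.35). Within that subset the more active patients still start nearer the cut-off.

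**Illustration 2: two states.** Let p be the proportion at target at index, s the probability of staying there and g the probability of gaining it, with s and g equal in both step groups. The 12-month rate is p·s + (1 − p)·g.

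| p, high vs low steps | s = 0.9, g = 0.3 | s = 0.7, g = 0.6 |
|---|---|---|
| 40% vs 30% | 54% vs 48%, OR 1.27 | 64% vs 63%, OR 1.04 |
| 50% vs 30% | 60% vs 48%, OR 1.62 | 65% vs 63%, OR 1.09 |
| 60% vs 30% | 66% vs 48%, OR 2.10 | 66% vs 63%, OR 1.14 |

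Example: 0.5 × 0.9 + 0.5 × 0.3 = 0.60, and 0.3 × 0.9 + 0.7 × 0.3 = 0.48. With equal p, or within levels of index status, the odds ratio is 1.00.

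**Would such a difference reach significance?** At r = -0.15 the difference is 0.364 − 0.237 = 0.127. With 100 patients per quartile the standard error is √[(0.237 × 0.763 + 0.364 × 0.636)/100] = 0.064, so power is Φ(0.127/0.064 − 1.96), about 50%. With 50 per quartile it is just under 30%. The document does not say how many patients will attend at 12 months.

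**The case against.** - **No wrong model is written down.** Objective 2 is a one-sentence hypothesis without thresholds, analysis set or model, and section 5.1 has no analysis of steps against targets. This stands. The fault is absent handling of the index value, not a stated erroneous method. It remains a point on this document, because the document itself holds the objectives, endpoints and analysis section and writes adjustment in for other questions.
- **Twelve-month status is a legitimate outcome.** The objective is worded as an association in a study described as explorative. Whether early steps identify patients who are at target a year later is a valid prognostic question without an index term. This also stands, provided the result is worded as being at target.
- **Section 3.2 may include earlier values.** It can be read that way, but nothing there uses them to define achievement, and the synopsis lists 12 months only.
- **The exposure may be steps after one year.** If the objective's heading governs, the description in terms of early steps does not apply as written. Relating 12-month steps to 12-month status still ignores the starting value, so the need for an index term remains.
- **A stronger reading is tempting:** that the hypothesis is bound to be confirmed for BMI, and probably for HbA1c, whatever steps do. The document does not support this. Every input is assumed, the effect is small at weak correlation or weak persistence, and power may be low. No calculation was made for HbA1c, systolic BP or LDL-C.

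**Conclusion.** The point holds as a gap in a secondary objective. Followed as written, the hypothesis counts patients already at target at the index PCI as achievers, and no planned analysis separates them from patients who reach target later. An association could appear with no relation between steps and change, most plausibly for BMI.

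The range shown is an odds ratio of about 1.2 to 4.4 for BMI under the assumed correlations, and 1.04 to 1.14 where target status persists weakly. These figures show the mechanism. They are not estimates for this cohort. The distortion depends on how far index status differs by step count and how strongly it persists, and the document gives neither. The sponsor should settle this before analysis.

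**What to change.** 1. In section 5.1, add a model of 12-month target status on steps for each measure, with the index value of the same measure as a covariate wherever the registry or the patient information system holds it (BMI at least).
2. As a supporting analysis, show patients not at target at index, keeping the index value as a covariate in that subset.
3. Where no index value exists, report the association as *being at target*, not *reaching* or *achieving* it.
4. Reconcile the exposure window: the synopsis and the objective's heading use steps after one year, the hypothesis the first two weeks.

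**Cost.** A few sentences in section 5.1 and one covariate per measure. The subset will be smaller. Section 8.2 plausibly covers index BMI, but does not show that numeric index systolic BP, LDL-C or HbA1c are held. Those values may be missing, and then step 3 applies.

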5.2. Handling of missing data and drop-outs

CARDIOBASE has very few missing cases for MACE, therefore, for MACE, a complete case analysis will be done. Activity data will be used when at least 7 days of 12 h/day (during day time) recording are available. Otherwise, these patients will be allocated to a non-compliant group for which patient characteristics will be summarised and compared to the compliant group. Patients of the non-compliant group will not be used for the analysis of the primary endpoint. For secondary outcomes, missing data will be imputed by multiple imputation.

In case of a large number of non-compliant patients (>50), additional patients will be recruited (if necessary recruitment period will be extended).

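### Hypothesis I of secondary objective 2 relates daily steps only to targets reached yes/no, although the measured 12-month values are the listed endpoints; for a roughly normal outcome the cut costs at least about 36% of the information

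*SAP*

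**What the plan says.** Secondary objective 2 appears in the synopsis and in SAP section 3.1 as "Association of daily steps after one year with reaching targets for systolic blood pressure", followed by LDL-C, BMI and HbA1c. Its Hypothesis I says that patients with more steps in the two weeks after discharge "have higher achievement rates of target levels at 12 months for blood pressure, body weight, blood lipids, and blood sugar". Both wordings make the outcome a yes/no variable for each measure.

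The endpoint list in section 3.2 has no target or cut-off: "Secondary endpoints: BMI, systolic BP, LDL-C, HbA1c and daily steps two weeks and 12 months after PCI". The synopsis likewise lists the four measures at 12 months.

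Section 5.1 has no model linking steps to target attainment. It says that "data on body mass index (BMI), systolic blood pressure (BP), low-density lipoprotein cholesterol (LDL-C) and smoking cessation will be derived" for patients with a yearly visit at the centre, and that these data will be "will be derived from the clinic's patient information system and compared between different forms of CR". HbA1c is not in that sentence. Section 5.2 adds: "For secondary outcomes, missing data will be imputed by multiple imputation".

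**The concern.** The four endpoints are numerical measurements that the study plans to have, yet the only hypothesis linking them to daily steps reduces each to reached or not reached. A patient just short of a target then counts the same as one far from it. The cut is least informative when nearly all or very few patients are at target.

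Because section 5.1 supplies no model, the hypothesis sentence is the only specification of this analysis. The values are available only "for patients who perform their yearly routine follow-up visit at our centre", a subset of unstated size out of about 825 recruits, and no power is claimed. At stake is avoidable loss of power to detect an association between steps and risk-factor control, using data already in hand.

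**Working it through.** **The plan's own figure.** The plan gives no sample size or power for this hypothesis. Its one powered figure concerns MACE: 4 × (1.960 + 0.842)² / (ln 2.66)² = 32.8, so 33 events in the two extreme quartiles, doubled to 66, and 66 / 0.08 = 825 patients. This reproduces section 5.1 but says nothing about objective 2.

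**Step 1: information kept by the cut.** For an approximately normal outcome linearly related to steps, cut so that a proportion p is at target, the efficiency relative to the full scale is E = φ(z_p)² / [p(1 − p)]. It is the same for p and 1 − p. It does not depend on the number of patients or, for weak associations, on the effect size.

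**Step 2: power after the cut.** If the full-scale analysis has 80% power at two-sided 5%, the yes/no analysis has Φ[(1.960 + 0.842) × √E − 1.960].

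| At target | E | Information lost | Power, from 80% |
|---|---|---|---|
| 50% | 0.637 | 36% | 61% |
| 30% or 70% | 0.576 | 42% | 57% |
| 20% or 80% | 0.490 | 51% | 50% |
| 10% or 90% | 0.342 | 66% | 37% |

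E is largest at p = 50%, so under this model the loss is at least about 36% wherever the target lies.

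**Step 3: loss in power points, illustrative only.** The number n of patients, the correlation r and the attainment rate are assumptions, since the plan states none of them. Full-scale power is Φ[√(n − 3) × atanh(r) − 1.960]; for the yes/no analysis r is replaced by r√E.

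| n | r | Full scale | Yes/no, 50% at target | Yes/no, 20% or 80% | Loss (points) |
|---|---|---|---|---|---|
| 100 | 0.10 | 16.6% | 12.1% | 10.2% | 4.5 to 6.4 |
| 200 | 0.10 | 29.1% | 20.1% | 16.5% | 9.0 to 12.6 |
| 200 | 0.20 | 81.2% | 61.8% | 50.7% | 19.4 to 30.5 |
| 400 | 0.10 | 51.6% | 35.7% | 28.7% | 15.9 to 22.9 |
| 400 | 0.20 | 98.1% | 89.4% | 80.2% | 8.7 to 17.9 |
| 800 | 0.10 | 80.9% | 61.7% | 50.8% | 19.2 to 30.1 |
| 800 | 0.20 | 100.0% | 99.5% | 97.8% | 0.5 to 2.2 |

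Simulation with 1,500 runs per setting agrees. For n = 200 and r = 0.20, full-scale power was about 82%, against 64% (50% at target) and 51% (80% at target). For n = 400 and r = 0.20 it was about 98%, against 90% and 80%.

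**Step 4: step period.** Objective 2 refers to steps one year on; its own Hypothesis I refers to the two weeks after discharge. The choice changes both the question and the number of patients, because sections 3.3 and 4.4 make the second tracking voluntary and tie it to the 12-month check-up.

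**The case against.** The strongest reply is that attainment is the question being asked. The synopsis and section 3.1 both speak of reaching targets, and whether more active patients reach them is a legitimate clinical question. This stands: the choice costs efficiency and is not an error in itself. It is also no reason to drop attainment, which can be reported next to the full-scale analysis.

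A reader might infer that section 3.2 contradicts the hypothesis. It does not: a target is judged from a measured value, and section 3.2 does not say how the values are to be analysed. A reader might also count the absence of numerical targets as a defect. They may stand in a protocol that is not at hand, so no weight is put on it.

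It is also true that section 5.1 fixes no test for this hypothesis, so the yes/no analysis is inferred from the hypothesis wording. Nothing in the plan forbids a supplementary analysis of the values. Finally, the study calls itself explorative and only the primary endpoint is powered. That limits the weight of the point, though exploratory work also gains from using the full scale.

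**Conclusion.** The point holds as an improvement to one secondary hypothesis. If the outcome is roughly normal and linearly related to steps, analysing target reached yes/no loses at least about 36% of the information, 51% at 20% or 80% attainment and 66% at 10% or 90%. Skewed values would need transforming before these figures apply.

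Two stronger readings are not supported. The first is that this trial loses a known number of power points. The range of about 9 to 31 needs roughly 200 to 400 patients, a correlation of 0.10 to 0.20 and 20% to 80% attainment, none of which the documents give; at 800 patients and a correlation of 0.20 the loss is only 0.5 to 2.2 points. The second is that the cut makes a false negative likely. At 400 patients and a correlation of 0.20 the yes/no analysis still has 80% to 89% power, while at 200 patients and 0.10 even the full-scale analysis has only 29%. The cut raises the chance of missing an association; by how much cannot be settled from the plan.

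The mismatch in step period is plain from the text and needs no assumption. The primary analysis and the 825-patient target are unaffected.

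**What to change.** In objective 2 and section 5.1, make the main analysis of Hypothesis I a regression of each measured 12-month value (systolic BP, LDL-C, BMI, HbA1c; transformed if skewed) on daily steps as a continuous variable. Add HbA1c to the 12-month data named in section 5.1. Name the adjustment covariates: section 5.1 plans none for this objective, but age, risk factors and comorbidities are already used elsewhere in the plan and could serve. Report target attainment alongside as a supportive result.

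In the same edit, state one step period in both the objective and its hypothesis.

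The cost is wording only; no new data or patients are needed. The downside is that the main effect becomes a mean difference per step increment instead of an attainment rate, which is why attainment should stay in the report.
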